9.2. Proposed Analysis

Data will be analysed using SPSS (latest version available at the time of analysis). Data will be presented descriptively and comparisons will be made among 3 groups. Parametric and non-parametric statistical tests will be applied for normally and non-normally distributed data, respectively.

Care home survey data will be analysed using descriptive analysis to estimate the secondary objectives. Textual data will be transcribed verbatim and themes will be derived using thematic analysis.

Questionnaire data will also be transcribed verbatim and summarised based on emerging theme bases on experiences and views of participants (when able to provide consent), carers and family members.

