1.1. Rationale for Study

Hypothesis: The composition and/or diversity of the gut microbiota is different between healthy elderly and those with Alzheimer's dementia, who do or do not exhibit behaviour(s) that are challenging

The concept that inspires Ageing-GB is that our gut microbiota impact upon the gut-brain axis and thereby on behaviour. We need to understand the nature of that impact, the underlying mechanisms, and how changes in diet can reprogram our gut microbiota-brain axis to resolve or reduce clinical symptoms associated with Alzheimer's dementia.

However, there has been no published work that we are aware of to examine the gut microbiota profile in patients with Alzheimer's disease. Consequently, first we need to demonstrate the differences in microbiota profile between AD patients with or without behaviours that are more challenging to manage. We believe that our work will be fundamental to provide evidence to support dietary modification or supplementation as cost-effective and safe avenues for alleviating signs and symptoms of dementia in this vulnerable group and thus reduce the carer burden.

This study will require the co-operation of care home managers and staff, and will thus simultaneously assess the feasibility of performing a nutritional intervention study in this group of individuals, in this setting.

2. Study Objectives and Outcomes

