2.2. Outcomes

2.2.1. Primary Outcome

Differences in the composition and activity of gut microbiota between three groups.

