7.1. Data Collection

Faecal samples will be analysed for SCFA profile and DNA bacterial profile. Samples will be stored with anonymised labels for up to 10 years. The volunteer phenotype (informing the study group) will be recorded on the CRF. Consent will be sought from subjects to collect faecal samples. Samples from Aberdeen nursing homes will be collected to maintain/ensure sample quality and integrity. These will be collected from the care home by one of the research staff from the Rowett Institute. All food diaries and other questionnaires will be anonymised following recruitment, and stored in a locked filing cabinet in the care home manager's office prior to collection by study researchers. Final storage will be locked filing cabinets in Human Nutrition Unit, or on a secure shared drive, accessible only by the researchers and auditors of the sponsor (for auditing purpose).

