9.1. Sample Size Calculation

We have examined existing data held at RINH with the statisticians from Biomathematics and Statistics Scotland (BioSS) on gut bacteria in faecal samples. The power calculations indicate that with 20 volunteers on a controlled diet the sample will provide at least 90% power to detect shifts of 20% or more in SCFA and metabolites, and a difference of 45% or more in bacteria between groups. Previous studies have shown that such shifts are achievable in healthy and diseased patient groups.

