9.3. Missing Data

The two time points in this study will be used to show consistency of microbial profiles within an individual. If there are missing data points then a reduced dataset of the double time points will be analysed, and an additional analysis of single time points will be made. Having double collection times from each individual will also test the feasibility of the collection process for the main study. We will collect menus from both weeks preceding sample collection in order to have some dietary record in the immediate run-up to sample collection.

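### The primary outcome is two whole profiles compared among three groups, with no primary measure, significance level or multiplicity control (2.2.1, 9.2); nor is it said how two samples per person enter that comparison

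*Combined protocol and SAP*

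**What the plan says.** The primary outcome in 2.2.1 is: "Differences in the composition and activity of gut microbiota between three groups". Section 7.1 gives the readouts: "Faecal samples will be analysed for SCFA profile and DNA bacterial profile". Each is a set of variables.

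The quantitative analysis in 9.2 consists of the choice of software and two sentences: "Data will be presented descriptively and comparisons will be made among 3 groups" and "Parametric and non-parametric statistical tests will be applied for normally and non-normally distributed data, respectively". No test is named. Neither 9.2 nor any other section names a primary variable, a global test, a significance level, an order of contrasts or a multiplicity rule.

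The target is worded differently from place to place. The hypothesis in 1.1 (Rationale for Study) begins: "The composition and/or diversity of the gut microbiota is different between healthy elderly". Section 2.2.1 has activity where the hypothesis has diversity. Section 9.1 speaks of SCFA, metabolites and bacteria, and says that "the sample will provide at least 90% power to detect shifts of 20% or more in SCFA and metabolites". The Rationale also offers two candidate lead contrasts: healthy elderly against Alzheimer's dementia, and, within dementia, "first we need to demonstrate the differences in microbiota profile between AD patients with or without behaviours that are more challenging to manage".

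Each participant gives two samples (3.1). Section 9.3 assigns the two time points to within-person consistency and to testing the collection process. If data are missing, "a reduced dataset of the double time points will be analysed, and an additional analysis of single time points will be made".

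**The concern.** The study states a hypothesis, has a comparative primary objective and claims power, so a reader will take a nominally significant group difference as an answer to the primary question. Under 9.2 as written, every SCFA and every taxon may be tested, with any or all of the three contrasts. Some significant results are then likely even if the groups do not differ, and nothing in the plan separates a planned result from a chance one. The summary and 9.4 say that the data will support a grant application, which the summary describes as a dietary intervention study. A chance difference could therefore set the target of that study.

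The smaller issue is that two values per person can be averaged, modelled together or analysed week by week. The plan does not say which of these answers the group comparison, even when no sample is missing.

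**Working it through.** **Inputs from the protocol.** 20 participants per group and three groups (3.1, 4.1); at least 90% power for shifts of 20% in SCFA and 45% in bacteria (9.1); two samples per person (3.1).

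**Assumptions, not in the protocol.** Two-sided 5% tests; 10 to 30 variables; correlation 0 or 0.5 between variables; intraclass correlation (ICC) 0.5 to 0.8 between a person's two samples; 10% to 30% of second samples missing at random.

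**1. The 90% figure.** Section 9.1 gives no SD, significance level or test, so the figure can only be inverted. For one two-sided 5% t-test with 20 per group, 90% power needs a standardised difference of 1.05 (noncentral t). The implied coefficients of variation are 0.20/1.052 = 19% for SCFA and 0.45/1.052 = 43% for bacteria. This holds for a single test. The 1.05 SD is used below as the difference of interest.

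**2. One measure, three uncorrected pairwise tests.** If independent, the chance of any false positive is 1 − 0.95³ = 14.3%. The contrasts share groups, and simulation gives about 12%.

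**3. Many variables.** The chance of at least one false positive when no group differs, with one omnibus test per variable at 5%, is 1 − 0.95^k for k independent variables:

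| Variables | Omnibus, independent | Omnibus, correlation 0.5 (simulated) |
|---|---|---|
| 10 | 1 − 0.95¹⁰ = 40% | 29% |
| 30 | 1 − 0.95³⁰ = 79% | 52% |

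One uncorrected omnibus test for each of just two domains (composition, activity) gives 1 − 0.95² = 9.8% if independent.

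**4. Error control under the proposed testing order.** With three groups, the omnibus test at level α guards the case where all are equal. If exactly one pair is equal, only one true null hypothesis remains among the pairwise tests, and it is tested at α. Simulated family-wise error is 4.9% for one measure, and 4.6% to 5.0% for two measures at 2.5% each.

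**5. Power under that order** (1.05 SD, one value per participant, simulated; 90% for a single unadjusted test):

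| Pattern | One measure at 5% | Two measures at 2.5% each |
|---|---|---|
| One group differs, largest contrast | 88% | 81% |
| Graded shift, largest contrast | 83% | 74% |
| Graded shift, group (i) v (ii), 0.53 SD | 36% (37% without the omnibus step) | 26% |

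**6. Benjamini-Hochberg for the rest.** Omnibus power for a variable that truly differs by 1.05 SD in one group falls from about 93% to 72% if 1 of 10 differs, and to 58% if 1 of 30 does. With 30 variables and 1 or 3 true differences, the expected false discovery rate is 4% to 5%, against 22% to 49% unadjusted. Both are averages over studies that count a study with no discovery as zero. Among studies that do report a discovery, the false share is higher.

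**7. Two samples per person.** With proportion m of second samples missing, the effective number per group is 20(1 − m)·2/(1 + ICC) from complete pairs, and 20m more if single samples are also used. Example, ICC 0.5 and m = 0.3: pairs 20 × 0.7 × 1.333 = 18.7; all samples 18.7 + 6 = 24.7.

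| ICC | Missing | Power, pairs only | Power, all samples | Loss (points) |
|---|---|---|---|---|
| 0.5 | 10% | 94.3% | 95.9% | 1.6 |
| 0.8 | 10% | 89.8% | 92.5% | 2.7 |
| 0.5 | 30% | 87.1% | 94.9% | 7.8 |
| 0.8 | 30% | 80.6% | 92.0% | 11.4 |

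These losses apply only if complete pairs were used for the group comparison.

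**The case against.** **It is a 60-person study with a feasibility aim.** The summary says that it will provide initial data, and 9.2 begins with description. This carries weight: an exploratory label with estimates and intervals would be a full answer. It does not remove the point, because feasibility is the secondary objective, the primary objective is comparative, and no section calls the group comparison exploratory.

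**Section 9.3 may not concern the group comparison.** A reader might infer that the primary comparison is to be confined to complete pairs, with the loss of power and possible bias that this brings. The text does not support that. Section 9.3 opens with within-person consistency, for which complete pairs are needed, and its missing-data rule may serve that purpose alone. Nor does it license a free choice between two results: the word *additional* suggests that the paired analysis leads. What stands is that neither 9.2 nor 9.3 says how two values per person enter the comparison.

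**Using all samples does not repair everything.** This is correct. Section 6 destroys all data and samples of anyone who withdraws, and replaces the person. Those first samples cannot be recovered by any model, so the gain applies only to participants who stay in and miss a sample. If loss depends on the value that was not observed, a mixed model reduces the bias but does not remove it.

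**The number of variables is not in the protocol.** This is also correct, and the 40% to 79% rests on an assumed range. The 12% for a single measure with three pairwise tests does not depend on it.

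**Conclusion.** The point holds for 2.2.1 and 9.2. Two multi-component profiles are the primary outcome, compared among three groups, with a stated hypothesis and a power claim but no primary measure, significance level or multiplicity control. At an assumed two-sided 5%, the false-positive risk is about 12% for one measure with three uncorrected pairwise tests. For one omnibus test per variable over 10 to 30 variables, it is 40% to 79% if they are independent and 29% to 52% at correlation 0.5. This goes beyond missing detail, because following 9.2 as written can produce positives that cannot be told from chance.

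The point on the two samples is secondary: a gap in specification. Only if complete pairs were also used for the group comparison would power suffer, by 2 to 3 points with 10% of second samples missing and 8 to 11 points with 30% (assumed ICC 0.5 to 0.8, 1.05 SD, missing at random). The protocol does not say that they would be.

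The change should be made before the group data are analysed. The feasibility aims are not affected.

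**What to change.** Choose (a) or (b); they are equally acceptable.

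**(a) Confirmatory.** In 2.2.1 name one primary measure, or one for composition and one for activity, each tested at 2.5%. Say whether diversity is primary or exploratory. In 9.2 add: *For each primary measure the three-group omnibus test comes first. Pairwise contrasts are tested at the same level only if it is significant. All other taxa and SCFAs are exploratory, with Benjamini-Hochberg at 5%.*

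**(b) Exploratory.** State in 2.2.1 and 9.2 that all group comparisons are exploratory and are reported as estimates with 95% confidence intervals, with Benjamini-Hochberg applied to any p-values shown.

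**In either case:**
- Add to 9.2 or 9.3: *The group comparison uses every available sample with the participant as the unit (a random-intercept mixed model, or rank tests on participant means). The choice for each outcome is fixed before group data are seen. Complete pairs are used only for within-person consistency.*
- Restate 9.1 so that the 90% is given per single test, or recompute it under the chosen rule.

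**Cost.** Wording in 2.2.1, 9.1, 9.2 and 9.3 and some analysis work; no new participants or data. Under (a), at an assumed 1.05 SD and one value per participant, power for the largest contrast falls from 90% to about 83% to 88% with one primary measure, or 74% to 81% with two. Benjamini-Hochberg costs more for exploratory variables: about 58% omnibus power if 1 of 30 truly differs. Option (b) gives up any confirmatory result.

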3.1. Study Description

An observational case-controlled study with three groups of participants with 1:1:1 will be carried out. A total of 60 volunteers, 20 in each group from the following groups (i) Alzheimer's dementia and challenging behavioural symptoms, (ii) Alzheimer's dementia and no challenging behavioural symptoms, (iii) without any type of dementia, will be recruited from care homes.

Each volunteer (assisted by staff) will provide two faecal samples, at least a week apart which will be analysed for microbial composition and activity by assessing Short Chain Fatty Acid profile (SCFA profile). Faecal samples will be collected using a pot on a toilet/commode, which will be sealed and processed in the laboratory within 12hr.

Additional information on regular diet composition will be collected by accessing the weekly care home menu. Staff will observe participants and record every episode which requires staff intervention as a result of behaviours that are challenging to manage.

A quality of life questionnaire will be completed by each volunteer in Alzheimer's dementia groups using DEMQOL (Dementia Quality of Life questionnaire).

DEMQOL is widely used patient reported outcome measures (PROMs) of health related quality of life in people with dementia.

Finally, we will collect other information on medication, personal characteristics, co-morbidities etc. to mitigate any confounding effects.

To achieve the secondary objectives the following outcomes will be assessed.

We will collect information on the following key aspects of feasibility of a larger study (future clinical trial) based on the main hypothesis driven work carried out under aim 3 described below

- (1) Proportion of eligible older people with Alzheimer's dementia with or without challenging behaviours
- (2) Proportion of eligible participants willing to participate
- (3) Proportion of participants who are able provide samples in each group
- (4) Proportion of participants (staff who are looking after them or relatives) who are able to provide study data /information

We will assess participants, their carers and whenever relevant managers and staff of care home and relatives/family members and people with Alzheimer's dementia with regard to willingness to participate in a research trial and to identify issues to be addressed to gain support for such an intervention trial through end of study questionnaire conducted by the study research nurse face to face.

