4.2. Inclusion Criteria

Resident in a care home

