5.3. Screening for Eligibility

In order to be recruited into study group (i) or (ii) there has to be an existing medical diagnosis of Alzheimer's dementia that will be confirmed by cross-referencing with medical records. Likewise for recruitment to group (iii) no such diagnosis should exist. The sub-group stratification of Alzheimer's dementia patients with or without behaviours that are challenging will be ascribed after speaking to care home staff and analysing care home records of participants.

Eligibility will be determined based on the knowledge of care home manager and staff. At this stage, the research team will not have any knowledge of who they are. Potentially eligible participants will first be approached by care home manager/staff to enquire whether they would be willing to speak to research team. Only those who are willing to speak to research team will be approached by the research nurse and provide study information. If they are interested and provide permission to check the eligibility, the diagnosis will be checked against their care home records. In case if the care home staff deem the potential participant lacks capacity, formal capacity assessment will be carried out by medically trained research team member.

Initial screening for eligibility will be carried out by care home staff and second level screening by study team will only happen after the participant has provided informed verbal consent prior to participation. If eligible written informed consent will be taken for study procedures.

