5.4. Ineligible and Non-Recruited Participants

Only eligible volunteers will be recruited to the study, up to the required number in each group. Once this number is reached, any additional interested volunteers will be thanked for their interest. No data will be collected prior to recruitment.

6. Withdrawal Procedures

If any participant wishes to withdraw from the study at any point after recruitment, all data and samples collected will be destroyed. If the carer perceives that participation in the study is causing distress to the volunteer, they will provide advice but if the distress persists the volunteer may be withdrawn from the study. In both cases a 'withdrawn from study' form will be completed and attached to the CRF. Unless such a form is completed (by either the volunteer or their representative) and consent is thus withdrawn, all samples will be kept following appropriate study guidelines. As the study requires 20 participant in each arm of the study, we will replace the withdrawal with further recruitment.

7. Data Collection and Management

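### Section 3.1 collects covariates to control confounding, but section 9.2 states no use of them for that purpose

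*Combined protocol and SAP*

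**What the plan says.** Section 3.1 gives the design: "An observational case-controlled study with three groups of participants with 1:1:1 will be carried out". It also gives the purpose of the additional data: "Finally, we will collect other information on medication, personal characteristics, co-morbidities etc. to mitigate any confounding effects". The matrix in section 3.2 schedules demographics, co-morbidities, medications and the Mini Nutritional Assessment at enrolment.

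The group comparison is described in two sentences of section 9.2: "Data will be presented descriptively and comparisons will be made among 3 groups", and "Parametric and non-parametric statistical tests will be applied for normally and non-normally distributed data, respectively". The rest of 9.2 deals with survey and questionnaire text. Section 9.1 covers sample size, and section 9.3 covers the two sampling times and missing samples. Neither mentions a covariate.

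Groups are formed by diagnosis and by information from the care home. Presence or absence of challenging behaviour "will be ascribed after speaking to care home staff and analysing care home records of participants". For the controls, section 5.3 says: "Likewise for recruitment to group (iii) no such diagnosis should exist". The only inclusion criterion in section 4.2 is "Resident in a care home". Section 5.4 fills each group to its quota: "Only eligible volunteers will be recruited to the study, up to the required number in each group". The opening summary describes the controls as healthy and matched on age.

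**The concern.** Nothing in the design makes the three groups alike except care-home residence and the exclusions in section 4.3 (recent antibiotics, active gastrointestinal disease, inability to consent). Age, other medication and other co-morbidities can differ between groups and may also be related to the gut microbiota. Collecting such variables does not control for them; an analysis has to use them.

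If 9.2 is run as written, a difference due to age or another measured characteristic could be read as an effect of dementia or of challenging behaviour. The group comparison is the primary objective (2.1.1), and its result is meant to support a later dietary intervention study. If adjustment is decided only after the data are seen, with several candidate covariates and 60 participants, the adjusted result carries less weight than one fixed in advance.

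**Working it through.** **Text check.** The purpose and the analysis, side by side:

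| Section | Content relevant to confounding |
|---|---|
| 3.1 | Medication, personal characteristics and co-morbidities collected to mitigate confounding |
| 9.1 | 20 volunteers, power and detectable shifts; no covariate |
| 9.2 | Three-group comparison, test chosen by normality; no covariate, model or stratification |
| 9.3 | Two sampling times and missing samples; no covariate |
| 4 to 5.4 | Care-home residence, three exclusions, groups by diagnosis and staff information; no matching or age limit |

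The purpose stated in 3.1 therefore has no stated analysis that serves it, and the design does not supply the control instead.

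**The plan's own figure.** Section 9.1 claims at least 90% power for shifts of 20% (SCFA and metabolites) and 45% (bacteria). It gives no SD, alpha, sidedness or test, so the claim can be neither reproduced nor refuted. The work below uses only n = 20 per group, a two-sided 5% level as an assumption, and SD units (within-group SD of the outcome).

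**Size of bias that matters.** For a t test of 20 v 20 (38 df), the rejection rate at a difference d is P(F′ > F₀.₉₅;₁,₃₈), where F′ is noncentral F with noncentrality 20d²/2 = 10d².
- 90% power is reached at d = 1.052.
- With no true effect, a bias of d = 0.212 raises the rejection rate from 5% to 10%. That is 0.212/1.052 = 20% of the difference detectable with 90% power.
- For the three-group F test (2 and 57 df) with one group shifted by d, the noncentrality is 20 × d² × 2/3, and 10% is reached at d = 0.222.

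**Illustration with age (all inputs assumed).** No true group effect. The controls differ in mean age by m SD, the within-group age-outcome correlation is r, and the bias is m × r.

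| m | r | Bias (SD) | t test, 20 v 20 | Three-group F |
|---|---|---|---|---|
| 0.5 | 0.3 | 0.15 | 7.5% | 7.2% |
| 0.5 | 0.5 | 0.25 | 12.0% | 11.4% |
| 1.0 | 0.3 | 0.30 | 15.2% | 14.5% |
| 1.0 | 0.5 | 0.50 | 33.8% | 33.7% |

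These are exact noncentral F values. Simulation gave 7.4% to 34.0% for the t test and, for Kruskal-Wallis, 6.4% to 32.3%. Adjusting for age and sex returned 5.0% in all four cases, but by construction, because age was the confounder and acted linearly. If the measured covariate correlates only 0.7 with the true confounder, the adjusted rates are 5.5%, 7.0%, 7.7% and 12.5%: lower, but not 5%.

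**Cost in power.** For a true contrast of 1.052 SD in the three-group model, unadjusted power without confounding is about 90.5%. Power after adjusting for age and sex (60 − 3 − 2 = 55 df):

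| Age gap | r = 0 | r = 0.3 | r = 0.5 |
|---|---|---|---|
| 0.5 SD | 87.8% | 90.8% | 95.1% |
| 1.0 SD | 84.1% | 87.2% | 92.6% |

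The largest loss occurs when age explains nothing, in which case it cannot confound either.

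**The case against.** Section 9.2 is short and does not rule out an adjusted analysis. Its descriptive presentation could include a table of these variables by group. A reader might therefore infer that the plan makes no use of the data at all, or that it forbids adjustment; the text supports neither. What stands is narrower: no use for confounding control is stated, and a table by group does not adjust anything.

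The harm figures rest on assumptions. The documents give no age gap and no age-outcome correlation, and the 0.21 SD threshold applies to any 20 v 20 t test. A reader might take 34% as this study's error rate, but it is the worst corner of an assumed grid. The illustration also shifts only the controls. The contrast between dementia with and without challenging behaviour, which the rationale says must be shown first, has no bias in that scenario.

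It is tempting to turn 0.212 SD into a percentage through 9.1. With increases of 20% and 45% on a log scale, the SDs are ln(1.20)/1.052 = 0.173 and ln(1.45)/1.052 = 0.353, giving spurious shifts of exp(0.212 × SD) − 1 = 3.7% and 7.8%. Section 9.1 does not support this as a bound. It gives no direction, and falls of 20% and 45% give 4.6% and 12.8%. Its 20 volunteers on a controlled diet could also describe a paired comparison, which sets no bound on between-person SD.

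Finally, this is a small study meant to supply feasibility and initial data. That limits the seriousness but does not answer the point, because the comparison is the primary objective and 9.1 claims formal power for it.

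**Conclusion.** The concern holds in this form: section 3.1 states a purpose of controlling confounding, sections 9.1 to 9.3 state no analysis that does so, and sections 4 to 5.4 contain no step that delivers age-matched controls. This rests on the text alone and needs no assumption.

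The possible size is illustrative. Given 20 per group and a two-sided 5% test, a bias of about 0.21 SD is enough to double the false-positive rate. Whether a bias of that size will occur cannot be derived from the documents, and they do not support a claim that the study is biased. The 7% to 34% range depends on the assumed age gaps and correlations and applies only to contrasts with the controls. Adjustment would reduce confounding by what is measured; it would not guarantee its removal. The change should be made, but the omission does not invalidate the study.

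**What to change.** 1. **Section 9.2.** State that each SCFA and bacterial outcome, taken as the participant's mean over the available samples on a scale fixed before the data are seen, will be compared among the three groups in a linear model adjusted for age and sex, with unadjusted tests alongside. Add one sensitivity model with a few medication, co-morbidity and nutritional covariates, each named before the data are seen. Label it exploratory, because some of these may be mediators or consequences of group membership. With five such covariates, 60 − 3 − 2 − 5 = 50 residual df would remain.
2. **Matching.** State how controls are matched on age, or delete the phrase from the summary.

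The cost is protocol wording. Age and sex are assumed to be within the demographics already scheduled in 3.2, and SPSS fits the model. The downside is the power loss shown above if age and sex explain little variance but differ between groups: from about 90% to 88% at an age gap of 0.5 SD and 84% at 1.0 SD, for a contrast of 1.05 SD.

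Two minor, separate points arise from the matrix in 3.2:
- Medications are scheduled at enrolment only, so no record is scheduled of antibiotics started between enrolment and the samples, although the Background names antibiotics as a modifier of the microbiota. Record this at each sample; it costs one question.
- The food menu is marked at enrolment only, whereas 9.3 promises menus from both weeks before sampling. The two sections should be reconciled.
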